It is well-known that MS clinical disease activity abates during pregnancy, although the mechanism(s) of these changes are not understood. Investigations of estrogens and progesterone have not provided consistent data supporting their potential role in MS protection during pregnancy. Relaxin (RLX), a peptide member of the insulin superfamily, is dramatically up-regulated and plays an important role in pregnancy. It also is an immune regulator and may contribute to the autotolerance that seems to develop during pregnancy in females with MS. The data that supports a potential role for RLX as an auto-immune mediator, and a potential therapeutic agent in multiple sclerosis, is presented in the paragraphs that follow.

Perioxisomal Proliferator-activated Receptor-Gamma (PPARG):

PPARG is part of a superfamily of nuclear hormone, ligand-activated transcription factors, that are receptors with DNA-linked and C-terminal ligand-linked domains ¹¹. Ligand activation of these receptors results in reduced pro-inflammatory and increased anti-inflammatory gene expression. PPARG is also constitutionally expressed on T-cell lymphocytes and macrophages in the periphery¹², on

astrocytes and microglia within the CNS, and may not only regulate systemic immune responses, but also regulate inflammatory responses within the CNS¹³. PPARG agonists reduce T-cell proliferation ¹⁴, inhibit production of the proinflammatory cytokines IL-1B, IL-2, IL-6, IL-12 ¹⁵, interferon gamma (IFNG) and TNFa ¹⁴, and promote T-cell apoptosis ^{14, 16}. PPARG ligand agonists also inhibit expression of IFNG-stimulated pro-inflammatory chemokine production by endothelial cells¹⁷, thus potentially inhibiting inflammatory cell trafficking.

Thiazolidinedone (TZD) anti-glycemic agents, such as pioglitazone and rosiglitazone, are PPARG agonist ligands that have both antiglycemic and antiinflammatory properties ¹⁶. Pioglitazone and rosiglitazone inhibit mitogenstimulated T-cell proliferation, as well as TNFa and IFNG production¹⁴.

In experimental allergic encephalomyelitis (EAE), used as an animal model of MS, TZDs reduce lymphocyte proliferation and infiltration into the CNS¹⁸, block IL-12-induced TH0 differentiation into pro-inflammatory TH1 T cells¹⁹, reduce gene expression for IL-1B and IL-6, reduce production of TNFa and IFNG, and reduce clinical disease expression ¹⁴.

PPARG knockout mice are more susceptible to developing EAE¹⁵, and PPARG antagonists block the neuroprotective effects of the TZDs in EAE²⁰. In limited studies in MS patients, PPARG expression is reduced in peripheral immune cells and these cells have reduced responsiveness to PPARG agonists¹⁴.

Relaxin biology overview:

Relaxins (RLX) are members of the insulin-relaxin peptide family^{21, 22}, that do not bind to insulin receptors and have no effects on glucose metabolism ²³. RLXs have been shown to regulate uterine contraction and cervical growth and softening during pregnancy²⁴, are vasodilators and promoters of angiogenesis and may be protective in ischemic cardiovascular disease ²⁵. RLX may also affect immune function, promoting anti-inflammatory mechanisms. There are 3 known isoforms of RLX, RLX 2 being the most abundant circulating form in humans ²⁴. The gene responsible for RLX2 production is on chromosome 9²⁶, and is produced primarily in the corpus luteum of females, and heart, lung and kidney in males ²⁷. RLX acting via its receptor RXFP-1, increases cAMP production²² and nitric oxide production via NO synthetase²⁵.

Relaxin as an immune-modulating/regulating agent:

RLX increases PPARG transcription activity via the receptor Relaxin Family Petide-1 (RXFP-1)^{21, 23, 28}, without increasing PPARG mRNA or PPARG protein levels²⁸. RLX independently promotes PPARG via RXRP-1. In addition to its direct PPARG promoting effects, it also increases responsiveness PPARG to TZDs such as rosiglitazone²⁸. Given the known anti-inflammatory effects of PPARG promotion, this is one possible mechanism by which RLX impacts immune function. A second mechanism likely involves promotion of the glucocorticoid receptor (GCR) gene²⁹. Although found in cell nucleus, exogenous RLX can also

enter the cell nucleus and up-regulate GCR gene, leading to increased production of GCR protein, whereas corticosteroids down-regulate the production of GCR protein, thus creating a negative feedback that can be opposed by RLX competition for the GCR gene site. RLX blocks mitogen-induced production of IL-1, IL-6 and TNFa by macrophages via GCR gene activation, which can be blocked by the GCR inhibitor RU-486²⁹.

Despite laboratory data demonstrating the potential for RLX as an immune regulating molecule via PPARG²⁸ and GCR²⁹ pathways, and its safety in the limited settings in which it has been given to humans for treatment of systemic sclerosis³⁰ and ischemic heart disease ³¹, there have been no published preclinical or clinical studies addressing potential efficacy of RLX in inflammatory CNS disease, and only one presented abstract in which it was reported that patients diagnosed with MS had higher circulating levels of RLX, and reduced binding affinity to RXFP-1, when compared to normal controls, suggesting that the increase in circulating RLX was the result of loss of RLX-RXFP-1 regulatory feedback mechanisms. Further analysis revealed that there was structural abnormality in the MS patients' RLX due to a mutation in the B- chain binding cassette of RX ([name] and [name], personal communication).

RESEARCH STRATEGY

1. Because of the potential benefits of using a human molecule, with an encouraging safety profile, capable of regulating immune responses, we intend, in the future, to develop a therapeutic trial to assess the efficacy and safety of RLX in the treatment of patients with the relapsing form of MS. However there is no information available on such fundamental guestions as what serum and CSF levels of RLX are observed in patients with active versus stable relapsing MS, how these values compare to that found in human volunteers without MS or other inflammatory diseases, and whether RLX functions normally in subjects with active or stable MS. It is for this latter reason that we are proposing research to obtain baseline information on serum and CSF RLX levels in patients with MS, as well as to further study RXFP-1 receptor binding affinity for RLX in patients with active and clinically stable MS. Fortunately there are reliable, commercially available SIMOA assays to measure RLX serum and CSF concentrations and available cell-based RXFP-1 affinity assay systems.

PROTOCOL

Subjects:

All subjects will be age 18 to 60, non-pregnant females, since 65 to 80% of MS patients are female, and there are known gender differences in circulating RLX levels. Patients with known history of diabetes will also be excluded.

There will be 3 groups of subjects:

Group 1 will consist of 10 subjects with suspected MS, who have had a clinical attack within the last 12 weeks, have at least one gadolinium-enhancing lesion on brain or spinal cord MRI taken within the prior 4 weeks, and for which they have not received any immunomodulating or immunosupressant medication. Because a subject in this group may have had a lumbar puncture in an emergency dept or in-patient setting for diagnostic purposes, prior to the investigators becoming aware of the patient, consent may be obtained post LP in this circumstance, and the analyses performed on residual CSF and serum, provided it had been handled in a manner not to interfere with the validity of the analyses. These subjects will also have had a urine pregnancy test performed prior to any relaxin analyses being performed on their samples.

Group 2 will consist of 10 subjects with clinically stable definite MS, with no evidence of clinical relapse for at least the past 12 weeks, and have no gadolinium enhancing lesions on MRI in the prior 12 weeks. These subjects will fulfill the Revised (2017) McDonald's Criteria for the Diagnosis of MS.

Group 3 will consist of 10 subjects without evidence of inflammatory systemic or inflammatory CNS disease, who require CSF removal for some other cause, such treatment of benign intracranial hypertension or as part of the procedure for insertion of an intrathecal medication delivery system.

Study Procedures:

All subjects will sign an IRB-approved informed consent prior to undergoing any study procedures. For patients with reproductive potential, urine sample will be collected and processed with the priority of STAT for qualitative pregnancy testing. The results of the STAT urine pregnancy test will be reviewed by research staff and routed to the study physician. The LP will not proceed unless a negative urine pregnancy test is confirmed. The one exception to this will be in Group 1 patients who had already had LP performed on an emergency basis and in whom consent to analyze residual CSF and serum was obtained. In this latter instance pregnancy test result will be obtained before any relaxin analysis is performed. Every patient will provide blood sample within 24 hours before, or 24 hours after the LP. Whole blood (8-ml) will be processed and serum (5-mL) collected for study analysis. In the case of CSF removal for suspected MS (Group 1), lumbar puncture and CSF removal is not a departure from standard of diagnosis/care, however an additional 5 mL of fluid will be collected for the purpose of this study during the standard procedure. In the case of the non-MS controls (Group 3), CSF removal is a routine part of their therapy and no additional fluid will be removed (5 mL of their fluid will be used for this study). Lumbar puncture and CSF removal is not a routine part of the diagnosis or care of patients with stable MS (Group 2), and thus their informed consent would reflect the fact that they are volunteering for a clinically unnecessary invasive procedure. No patient in Group 2, with clinically stable MS, will be responsible for the costs of performing the lumbar puncture, whereas the patients in groups 1 and 3 would be having lumbar puncture in the routine course of the management of their disease, and thus the cost of the procedure should be borne by their insurer. The total volume of CSF for Group 2 is also 5 mL.

All study samples will be stored frozen before batch transport to Quanterix for testing.

Approximately 24 hours after the LP procedure research staff will contact the patient by phone to discuss any symptoms or serious adverse events. The outcome of the phone call will be routed to the physician and the patient will be encouraged to contact the study doctor with any additional questions or concerns. All SAEs will be reported the Institutional Review Board per institutional policy and guidelines.

Analysis:

Descriptive statistics will be applied to each variable show the distribution of the data. T-tests or nonparametric tests, depending on the type and distribution of the data, will be performed to compare the differences between groups.

Results:

Patients may be informed of the results of their study testing only after the completion and analysis of all study data.

CONFIDENTIALITY:

Each volunteer subject will be assigned a unique identification number, and this will be used to identify all samples sent to the diagnostic laboratory. The subjects' names, or any other personal identification information will never be available to the diagnostic laboratory or its members.

The results of the data will be returned to the primary investigators for analysis, identified by unique code only, and only after the data has been received will the group that each sample belongs to be identified. The sole individual who knows both personal identification and code numbers will always be blinded to the analytic results and will not share the identity of any subject with the other investigators.

ASSAYS

RLX 1 is measured in serum and CSF by DuoSet (R & D Systems # DY3257) sandwich ELISA. This method is RLX 1 specific and does not cross react with RLX 2, The range of sensitivity of the assay is from 100-10000 pg/mL., and is linear within this range.

RLX 2 is measured in serum and CSF by Quantikine (R & D Systems # DRL 200) sandwich ELISA. This method is RLX 2 specific and does not cross react with RLX 1. The range of sensitivity of the assay has been demonstrated to be 7.8 to 500 pg/mL and is linear within this range.

RLX-RXFP-1 affinity is measured as a function of cAMP production in human monocyte THP-1 cells expressing RXFP-1, following incubation with RLX 1 or RLX 2, both of which act as agonist ligands for this G protein-coupled receptor.

The cAMP levels will also be determined by a commercially available cAMP assay (Flash Plate RAI 125 cAMP assay-Perkin Elmer) in the presence and absence RX neutralizing antibodies. All RLX assays will be performed at Quanterix Labs, Lexington MA.

These analyses will provide us with quantitative data re: baseline RLXIevels in serum and CSF in subjects with and without known inflammatory CNS disease, as well as alterations in RLX receptor affinity that may occur, and determine whether there are differences in serum/CSF RLX levels and RLX receptor affinities during acute inflammatory and stable states in patients with the relapsing form of MS.

INSTITUTIONAL SUPPORT

The Providence Brain and Spine Institute's clinical research team consists of a manager, two full-time research nurses, five full-time clinical research coordinators (CRC), and 3 part-time clinical research assistants. In 2012, the team supported more than 30 active clinical trials in Alzheimer's disease, ALS, multiple sclerosis, Parkinson's disease, and stroke. The research staff has the experience and skills in conducting cooperative group trials, industry-sponsored trials, and investigatorinitiated studies. For each trial, the research staff works closely with the investigators to coordinate study activities, collect clinical research data, track patient and study status, and perform quality assurance activities regularly. The research team is familiar with clinical trials that require multiple specimen collections, diagnostic testing, and neurological and other clinical assessments. The MS Center has 4 full-time providers (5 MS neurologist and 1 NP) and a team of clinical support staff that take care of close to 3,000 MS patients. The group has successfully collaborated with industry and federally-funded sponsors, clinical research organizations, investigators, and ancillary services facilities on more than 30 MS studies in the past 5 years.

For the performance of the serum and CSF RLX and Sema4A levels and RXFP-1 RLX receptor affinity analyses, commercial and university laboratories will be employed as noted in the protocol.

REFERENCES

1. Weinshenker BG. Databases in MS research: pitfalls and promises. Mult Scler 1999;5:206-211.

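### Active and stable MS are also suspected and definite MS, so a Group 1 v Group 2 difference cannot be attributed to disease activity alone

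*Combined protocol and SAP*

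**What the plan says.** All references are to the combined protocol and SAP.

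- **Group 1 (PROTOCOL, Subjects).** "Group 1 will consist of 10 subjects with suspected MS, who have had a clinical attack within the last 12 weeks". They must also "have at least one gadolinium-enhancing lesion on brain or spinal cord MRI taken within the prior 4 weeks", with the further condition "for which they have not received any immunomodulating or immunosupressant medication".
- **Why Group 1 is sampled (Study Procedures).** "In the case of CSF removal for suspected MS (Group 1), lumbar puncture and CSF removal is not a departure from standard of diagnosis/care". The Subjects section adds that the puncture may already have been done for diagnosis in an emergency or in-patient setting.
- **Group 2 (PROTOCOL, Subjects).** "Group 2 will consist of 10 subjects with clinically stable definite MS, with no evidence of clinical relapse for at least the past 12 weeks". They must have no enhancing lesion over the same 12 weeks and must meet the 2017 McDonald criteria. No limit on time since onset or diagnosis is given, and no treatment restriction.
- **Shared eligibility.** "All subjects will be age 18 to 60, non-pregnant females", with known diabetes excluded.
- **Analysis.** After descriptive statistics, "T-tests or nonparametric tests, depending on the type and distribution of the data, will be performed to compare the differences between groups". No covariate, stratification or matching is mentioned.
- **Intended reading.** The paragraph closing the ASSAYS section says the data will show whether relaxin levels and receptor affinity differ between acute inflammation and stability in relapsing MS. RESEARCH STRATEGY asks the same question and presents the answer as groundwork for a later therapeutic trial.

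**The concern.** The study wants to know whether relaxin (RLX) or its RXFP-1 receptor affinity changes with disease activity. The two MS groups differ in activity, but by definition they also differ in where the woman stands in her diagnosis. No group contains diagnosed MS in relapse, and none contains suspected MS that is quiescent.

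Two further differences probably follow. Women under diagnostic work-up will tend to be earlier in their disease than women drawn from an established MS clinic, and may be younger. The protocol itself gives a reason to care about age: its relaxin biology overview names the corpus luteum as the main source of RLX2 in females, and the eligible range runs from 18 to 60. It already controls sex, pregnancy and diabetes by eligibility, and cites sex differences in circulating RLX as one reason for enrolling only women. It does nothing comparable for age or duration in the comparison where both may track the group label.

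At stake is the interpretation of the Group 1 v Group 2 result, and what is carried from it into the planned trial. The Group 2 volunteers accept a lumbar puncture that they do not clinically need, which is a further reason to make their comparison interpretable.

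**Working it through.** The plan states no alpha, power, effect size or SD, so it has no figure to reproduce. The check has three parts.

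**1. Which factors move together**

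| Factor | Group 1 | Group 2 | Overlap possible? |
|---|---|---|---|
| Activity | attack within 12 weeks, enhancing lesion within 4 | neither for 12 weeks | no, by design |
| Diagnostic status at entry | suspected | definite (McDonald 2017) | no, by definition |
| Time since first symptom | not limited; diagnostic setting suggests short | not limited | yes, extent unknown |
| Age | 18–60 | 18–60 | yes, extent unknown |

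**2. Whether adjustment could separate them**

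Take a model with an intercept, a group indicator and a stage indicator, 10 v 10. With diagnostic status as the stage, all 10 in Group 1 are suspected and all 10 in Group 2 definite. The correlation is r = 1 and the design matrix has rank 2 of 3, so the activity effect is not estimable.

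For a recent/established split of disease duration, some overlap is possible. The variance inflation is VIF = 1/(1 − r²), and the effective size per group is 10 × (1 − r²). The counts below are assumptions.

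| Subjects who overlap | r | VIF | Effective n per group |
|---|---|---|---|
| 1 recent-onset in Group 2 | 0.905 | 5.50 | 1.8 |
| 2 recent-onset in Group 2 | 0.816 | 3.00 | 3.3 |
| 3 recent-onset in Group 2 | 0.734 | 2.17 | 4.6 |
| 1 crossover in each group | 0.800 | 2.78 | 3.6 |
| 2 crossovers in each group | 0.600 | 1.56 | 6.4 |

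First row as an example: r = (10×9 − 0×1)/√(10×10×11×9) = 90/99.5 = 0.905, so 1 − r² = 0.182, VIF = 5.5 and effective n = 1.8.

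Even the unadjusted 10 v 10 comparison needs a true difference of about 1.32 SD for 80% power (t-test, two-sided 5%, both assumed). Adjustment after the event is therefore not a realistic remedy unless overlap is substantial.

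**3. What an uncorrected shift would do**

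Assume no activity effect and a mean shift of δ SD caused only by duration or age. The two-sample t-test has 18 degrees of freedom, critical value 2.101 and noncentrality δ × √(10/2) = 2.236 δ.

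| Assumed δ | Noncentrality | Probability of p < 0.05 |
|---|---|---|
| 0.3 | 0.67 | 9.7% |
| 0.5 | 1.12 | 18.5% |
| 0.7 | 1.57 | 31.7% |

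With no shift the figure is 5%.

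In the other direction, the shift subtracts from the true difference. A true 1.0 SD activity effect has 56.2% power. An opposing 0.5 SD shift leaves 1.0 − 0.5 = 0.5 SD, for which power is 18.5%. The mean difference falls by exactly the shift, but the loss of power (37.7 percentage points here) is not equal to the rejection rate in the table.

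**The case against.** The strongest reply is that the documents link neither RLX nor receptor binding to disease duration, and give no data linking either to age. That is right. The 0.3 to 0.7 SD shifts are hypothetical and the same percentages would follow from any imbalance of that size in a 10 v 10 study. They show sensitivity, not that bias exists.

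A reader might go further and infer that Group 1 is a first-presentation cohort and Group 2 a long-standing one, so that activity and duration cannot be separated at all. The text does not support this. It does not require a first attack, so a woman with earlier undiagnosed attacks may enter Group 1. A Group 2 subject may be little more than 12 weeks past her last relapse and recently diagnosed. Nothing says how the site will fill Group 2. Complete aliasing is established for diagnostic status only.

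A fixed cap on Group 2 duration is also open to objection. Any number of years would be arbitrary, it would narrow a study meant to inform a trial in relapsing MS generally, and every subject would still be either suspected or definite according to group. This stands, and no cap is proposed below.

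Finally, the design has a practical rationale: Group 1 punctures are already part of care, and the aim is baseline description. The protocol asks whether levels differ between states and does not claim that inflammation causes the difference. This limits the seriousness of the point. But naming the contrast by activity state alone still invites that reading, and no planned data item would let anyone test it.

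**Conclusion.** The point holds with defined limits. Activity is completely aliased with diagnostic stage, as a matter of definition and without further assumptions. Association of activity with disease duration and age is likely from the recruitment setting but not certain, and the plan neither prevents nor measures it. The unadjusted tests therefore cannot assign a Group 1 v Group 2 difference to activity alone.

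The size is unknown. The range of 10% to 32% false attribution rests on an assumed 5% two-sided t-test, equal SDs, no true activity effect and assumed shifts of 0.3 to 0.7 SD. The documents do not support saying that the comparison is biased by any particular amount, or that duration is inseparable from activity. The consequence is confined to interpreting this contrast in a small exploratory study, and the change is worth making before enrolment.

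**What to change.** 1. **Selection.** Choose Group 2 volunteers to match Group 1 by 10-year age band. Where more than one is available, prefer the shorter disease duration, without a fixed cap. Group 2 is recruited electively, so each volunteer can be selected after a Group 1 subject has been enrolled.
2. **Data.** Record date of first symptom in Groups 1 and 2.
3. **Analysis.** Report the Group 1 v Group 2 result alongside the duration and age distributions of each group. In view of the effective sizes above, do not rely on a covariate model to separate the factors.
4. **Conclusion.** Reword the closing statement of the ASSAYS section so that the contrast is suspected, untreated, active MS versus definite, stable MS, and say plainly that activity cannot be separated from diagnostic stage.

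The cost is one selection sentence, one data item and a narrower conclusion, with no added subjects or procedures. Group 2 recruitment would be somewhat slower. INSTITUTIONAL SUPPORT describes a centre with nearly 3,000 MS patients, but the documents do not show how many are eligible women willing to have an elective lumbar puncture. Matching reduces the age imbalance and may reduce the duration imbalance. It does not remove the suspected-versus-definite aliasing.

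### Group 1 excludes immune therapy while Group 2 has no therapy rule and no recording or adjustment is specified, so the active-versus-stable comparison of RLX levels may be confounded by treatment

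*Combined protocol and SAP*

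**What the plan says.** All references are to the combined protocol and SAP.

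- **Aim.** Research Strategy asks "what serum and CSF levels of RLX are observed in patients with active versus stable relapsing MS" and describes the purpose as to "obtain baseline information on serum and CSF RLX levels in patients with MS". The closing paragraph of Assays repeats the acute-versus-stable comparison as something the study will determine.
- **Group 1 (Subjects).** "Group 1 will consist of 10 subjects with suspected MS". Entry requires a recent attack, and on imaging they must "have at least one gadolinium-enhancing lesion on brain or spinal cord MRI taken within the prior 4 weeks". A restriction on medication is then added: "and for which they have not received any immunomodulating or immunosupressant medication".
- **Group 2 (Subjects).** "Group 2 will consist of 10 subjects with clinically stable definite MS", with no relapse and no enhancing lesion for 12 weeks. "These subjects will fulfill the Revised (2017) McDonald's Criteria for the Diagnosis of MS". Nothing requires, bars or limits immune therapy.
- **Criteria for all groups.** Age, sex, pregnancy and diabetes. Medication is not mentioned.
- **Study Procedures.** Consent, pregnancy test, blood sample, lumbar puncture (LP) and a telephone call about 24 hours later. No therapy history is listed.
- **Analysis.** Descriptive statistics for each variable, without a list of variables, then t-tests or nonparametric tests between groups. No covariate, stratum or subgroup is named.

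**The concern.** The two MS groups are meant to differ in disease activity. By their entry rules they can also differ in treatment: Group 1 is restricted and Group 2 is open. A difference in serum or CSF RLX, or the lack of one, could then reflect therapy, activity or both, and the planned test would still be read as an activity result. That result is intended to inform a later RLX trial in relapsing MS.

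The Group 1 restriction is itself unclear. It can be read as no such medication for this attack or as none ever, and it does not say whether corticosteroids count. That matters on the protocol's own account. The section on relaxin as an immune-modulating agent sets RLX and corticosteroids in opposition on the glucocorticoid receptor (GCR): RLX raises production of the protein, "whereas corticosteroids down-regulate the production of GCR protein".

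A minor related point is that Group 1 is suspected MS while only Group 2 must meet the 2017 McDonald criteria. A Group 1 subject who proves not to have MS would remain in the active-MS mean.

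**Working it through.** **Figures in the plan.** The documents give group sizes (10 each) but no alpha, SD, effect size or power, so there is no stated figure to reproduce. They also give no treated fraction and no effect of therapy on RLX. Everything below other than the group sizes is assumed: SD 1, two-sided 5% test, independent normal values.

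**1. Bias.** Let f1 and f2 be the treated fractions in Groups 1 and 2, and s the shift in RLX (in SD) among treated subjects. The expected Group 2 minus Group 1 difference is

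activity effect + (f2 − f1) × s.

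If Group 1 is fully untreated, f1 = 0 and the bias is f2 × s. It is zero if f2 = 0 or s = 0.

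**2. Rejection rate with no activity effect.** Simulated t-test, 10 versus 10:

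| Group 2 treated | Bias, s = 0.5 | Rejects, s = 0.5 | Bias, s = 1 | Rejects, s = 1 |
|---|---|---|---|---|
| 10% | 0.05 SD | 5% | 0.10 SD | 5% |
| 30% | 0.15 SD | 6% | 0.30 SD | 9% |
| 50% | 0.25 SD | 8% | 0.50 SD | 17% |
| 90% | 0.45 SD | 16% | 0.90 SD | 46% |
| 100% | 0.50 SD | about 18% | 1.00 SD | 56% |

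With s = 0 the rate is 5% whatever the treated fraction.

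**3. Masking.** Take an assumed true activity effect of 1 SD, with 70% of Group 2 treated and a 0.5 SD shift that moves Group 2 towards Group 1. The expected difference falls from 1 to 1 − 0.7 × 0.5 = 0.65 SD, and t-test power falls from 56% to 27%.

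**4. What recording could recover.** If Group 1 is untreated, the treated-versus-untreated comparison exists only inside Group 2. Adjusting for treatment then amounts to comparing Group 1 with the untreated part of Group 2. If k of the 10 are treated, the standard error is √(1/10 + 1/(10 − k)):

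- k = 0: √0.200 = 0.447 SD
- k = 5: √0.300 = 0.548 SD
- k = 8: √0.600 = 0.775 SD
- k = 10: not estimable

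The 95% CI half-width is t(0.975, df) × √(1/10 + 1/u), with u untreated subjects and df = 8 + u:

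- u = 10: 2.101 × 0.447 = 0.94 SD
- u = 5: 2.160 × 0.548 = 1.18 SD
- u = 3: 2.201 × 0.658 = 1.45 SD

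The chance of fewer than 3 untreated, from Binomial(10, 1 − f2), is 5%, 38% and 93% when the treated fraction is 50%, 70% and 90%.

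**The case against.** The strongest reply has four parts.

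- **No treatment effect on RLX is documented.** This stands. The corticosteroid statement concerns GCR protein; it does not say that any drug changes serum or CSF RLX, and it does not touch other immune therapies. The point is therefore about possible confounding of unknown size, and the larger rejection rates above belong to extreme pairs of assumed inputs.
- **The data may be captured anyway.** This partly stands. No case report form is in the text supplied, and Analysis does not list its variables, so the omission is from the plan as written and not proof that medication goes unrecorded. The code-holder described under Confidentiality can link samples to persons, so later chart review is possible in principle if consent allows it. Even so, no stated analysis would use the information.
- **This is a 30-subject baseline study.** It is, and the levels described within each group are unaffected. But the plan also tests between groups and names active versus stable as a question.
- **An untreated subgroup may be too small to help, and untreated stable patients may differ in other ways.** This stands, and it is why the comparison proposed below is descriptive.

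A reader might infer more: that the contrast cannot be separated from treatment at all. The documents do not support that. They allow treated Group 2 subjects without requiring them, and full confounding needs all ten to be treated. Nor does the concern extend readily to receptor affinity. Assays describes a readout in THP-1 cells, so therapy acting on a subject's own receptors would not enter it.

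**Conclusion.** The concern holds as a possible confounding of one stated comparison: serum and CSF RLX levels in Group 1 versus Group 2. It arises from an asymmetry in the entry rules, together with the absence from the text supplied of any therapy recording, adjustment or stratification. Confidence in that textual finding is high. The consequence is uncertain. With a 0.5 SD shift assumed, the effect on the test runs from negligible (about 5% rejection with 10% treated) to about 18% with all treated, and it vanishes if therapy does not affect RLX.

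The difference between suspected and definite MS is minor. Group 1 already requires an attack and an enhancing lesion, and the documents give no misdiagnosis rate from which to size it.

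This is a cheap improvement to how the comparison can be interpreted; it does not invalidate the study.

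**What to change.** 1. Clarify the Group 1 medication wording: whether it covers this attack or any past use, and whether corticosteroids count. No change to anyone's treatment is proposed.
2. For each MS subject, record at LP the current and past immune therapy, including corticosteroids, and the time since last dose.
3. Show Group 2 RLX values by treated and untreated status. Pre-specify Group 1 versus untreated Group 2 as a descriptive sensitivity comparison (estimate and 95% CI). If fewer than 3 are untreated, list individual values instead.
4. State that a Group 1 versus Group 2 difference, or its absence, will not be attributed to disease activity alone if treatment differs between the groups.
5. Minor: note each Group 1 subject's final diagnosis from the standard work-up where available, and report how many were confirmed as MS. The last planned contact is about 24 hours after LP, so check that consent covers later chart review.

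The cost is a few data fields and some wording, with no added procedure or sample. The subgroup comparison will be imprecise, so recording limits over-interpretation but may not repair the contrast.
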